7.1.4 Serious

An Unanticipated Problem or Protocol Deviation is serious if it meets the definition of a Serious Adverse Event or if it compromises the safety, welfare or rights of subjects or others.

7.1.5 Serious Adverse Event

An adverse event or suspected adverse reaction is considered serious if in the view of the investigator or the sponsor, it results in any of the following:

- Death,
- A life-threatening adverse drug experience
- Inpatient hospitalization or prolongation of existing hospitalization
- Persistent or significant incapacity or substantial disruption of the ability to conduct normal life functions
- A congenital anomaly/birth defect.
- Important medical events that may not result in death, be life-threatening, or require hospitalization may be considered a serious adverse drug experience when, based upon appropriate medical judgment, they may jeopardize the patient or subject and may require medical or surgical intervention to prevent one of the outcomes listed in this definition.

7.1.6 Disability

A substantial disruption of a person's ability to conduct normal life functions.

7.1.7 Life-threatening adverse drug experience

Any adverse event or suspected adverse reaction that places the patient or subject, in the view of the investigator or sponsor, at immediate risk of death from the reaction as it occurred, i.e., it does not include a reaction that had it occurred in a more severe form, might have caused death.

7.1.8 Protocol Deviation (NIH Definition)

Any change, divergence, or departure from the IRB-approved research protocol.

7.1.9 Non-compliance (NIH Definition)

The failure to comply with applicable NIH Human Research Protections Program (HRPP) policies, IRB requirements, or regulatory requirements for the protection of human research subjects.

7.1.10 Unanticipated Problem

Any incident, experience, or outcome that:

- Is unexpected in terms of nature, severity, or frequency in relation to
 - (a) the research risks that are described in the IRB-approved research protocol and informed consent document; Investigator's Brochure or other study documents, and
 - (b) the characteristics of the subject population being studied; **AND**
- Is related or possibly related to participation in the research; **AND**
- Suggests that the research places subjects or others at a *greater risk of harm* (including physical, psychological, economic, or social harm) than was previously known or recognized.

7.2 NCI-IRB AND CLINICAL DIRECTOR (CD) REPORTING

7.2.1 NCI-IRB and NCI CD Expedited Reporting of Unanticipated Problems and Deaths

The NCI PI will report in the NIH Problem Form to the NCI-IRB and NCI CD:

- All deaths, except deaths due to progressive disease
- All Protocol Deviations
- All Unanticipated Problems
- All non-compliance

Reports must be received within 7 days of PI awareness via iRIS.

7.2.2 NCI-IRB Requirements for PI Reporting at Continuing Review

The NCI PI will report to the NCI-IRB:

1. A summary of all protocol deviations in a tabular format to include the date the deviation occurred, a brief description of the deviation and any corrective action.
2. A summary of any instances of non-compliance
3. A tabular summary of the following adverse events:
 - All Grade 2 **unexpected** events that are possibly, probably or definitely related to the research;
 - All Grade 3 and 4 events that are possibly, probably or definitely related to the research;
 - All Grade 5 events regardless of attribution;
 - All Serious Events regardless of attribution.

NOTE: Grade 1 events are not required to be reported.

7.2.3 NCI-IRB Reporting of IND Safety Reports

Only IND Safety Reports that meet the definition of an unanticipated problem will need to be reported to the NCI IRB.

7.3 NCI GUIDANCE FOR REPORTING EXPEDITED ADVERSE EVENTS, PROTOCOL DEVIATIONS AND NON-COMPLIANCE FOR MULTI-CENTER TRIALS

7.3.1 Serious Adverse Events

DFCI PI, BIDMC PI and MSKCC PI must immediately report to the NCI PI and NCI Study Coordinator, using the mandatory MedWatch form 3500a, any serious adverse event, whether or not considered drug related, including those listed in the protocol or investigator brochure and must include an assessment of whether there is a reasonable possibility that the drug caused the event within 24 hours of PI awareness of the event.

If the event also needs to be reported using the CCR Problem Report Form ([APPENDIX E](#)), the NCI Study Coordinator will contact the participating sites (DFCI and MSKCC).

As the CCR is the IND Sponsor of the study, then in addition to reporting to the NCI PI the DFCI PI and MSKCC PI must submit the report to the CCR as per section [7.4](#).

7.3.2 Deviations, Unanticipated Problems and Non-Compliance

DFCI PI and MSKCC PI must report any protocol deviations, unanticipated problems, or non-compliance to the NCI PI within 7 days of PI awareness using the CCR Problem Report Form (See [APPENDIX E](#)). The report must be sent to their IRB in accordance with their institutional policies.

7.4 IND SPONSOR REPORTING CRITERIA

During the first 30 days after the subject receives investigational agent/intervention, the investigator must immediately report to the sponsor, using the mandatory MedWatch form 3500a, or equivalent, any serious adverse event, whether or not considered drug related, including those listed in the protocol or investigator brochure and must include an assessment of whether there is a reasonable possibility that the drug caused the event. For serious adverse events that occur more than 30 days after the last administration of investigational agent/intervention, only report those that have an attribution of at least possibly related to the agent/intervention.

Required timing for reporting per the above guideline:

Deaths (except death due to progressive disease) must be reported via email within 24 hours. A complete report must be submitted within one business day.

Other serious adverse events as well as deaths due to progressive disease must be reported within one business day

Events will be submitted to the Center for Cancer Research (CCR) at: [contact] and to the NCI PI and study coordinator.

7.4.1 Reporting Pregnancy

7.4.1.1 Paternal exposure

Male patients should refrain from fathering a child or donating sperm during the study and for one month after the last dose of PROSTVAC. Pregnancy of the patient's partner is not considered to be an AE. However, the outcome of all pregnancies (spontaneous miscarriage, elective termination, ectopic pregnancy, normal birth, or congenital abnormality) occurring from the date of the first dose until one month after the last dose should, if possible, be followed up and documented.

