- 2.1.1.16 The effects PROSTVAC on the developing human fetus are unknown. For this reason, men must agree to use adequate contraception (hormonal or barrier method of birth control; abstinence) prior to study entry, for the duration of study therapy and at least one month post therapy. Should a woman become pregnant or suspect she is pregnant while her partner is participating in this study, she should inform her treating physician immediately.

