3.7 CRITERIA FOR REMOVAL FROM PROTOCOL THERAPY AND OFF STUDY CRITERIA

Prior to removal from study, effort must be made to have all subjects complete a safety visit approximately 28 days following the last dose of study therapy.

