3.8 FOLLOW-UP EVALUATIONS

After subjects have stopped taking the study medication for any of the reasons listed in Section [3.7](#), they will be seen at the study site, if logistically feasible, for a safety visit within 4-5 weeks of drug discontinuation. The safety assessments may be performed by a local physician and laboratory if patients unable to return to the study site at this time.

The following assessments will be performed at the follow up safety visit:

- History and Physical Examination
- Serum chemistries (Na+, K+, Cl-, CO2, glucose, BUN, creatinine, albumin, calcium, magnesium, phosphorus, alkaline phosphatase, ALT, AST, total bilirubin, LDH, CK, uric acid, total protein)
- CBC/differential with platelet count
- Serum PSA level
- Serum PAP
- Adverse event reporting

After the safety visit, if there are no unresolved grade 3 or higher AEs, we may, when feasible contact the patient annually to find out how they are doing and to determine survival status. If there are unresolved grade 3 – 4 AEs, patients will be followed either at the study site or by their local physician. In the latter case, we will obtain the physician's record of AEs.

Any scans performed outside of the study site will also be obtained when possible.

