- *NIH Guidelines for Research Involving Recombinant DNA Molecules (NIH Guidelines). See current version at:*
http://osp.od.nih.gov/sites/default/files/NIH_Guidelines.html
- *Biosafety in Microbiological and Biomedical Laboratories; U. S. Department of Health and Human Services Centers for Disease Control and Prevention and National Institutes of Health. See current edition at:*
<http://www.cdc.gov/biosafety/publications/index.htm>

Patient Care Implications and Contraindications

Cover vaccination sites with a sterile dry dressing (e.g., Telfa pad). Once the injection site is healed, no further barrier is necessary. As a precaution, protect injection sites that are exhibiting evidence of weeping, oozing or ulceration with a sterile dry dressing. In these circumstances, instruct patients to avoid direct contact of the injection site with susceptible individuals (e.g.; those who may be immunocompromised by disease or therapy). Instruct patients to avoid fathering a child for at least 4 months following therapy completion with the recombinant vaccine. Instruct patients receiving fowlpox vaccines to avoid direct contact with pet birds for at least 72 hours after vaccination or while there are any visible lesions at the injection site.

Due to the method of manufacturing (virus grown in primary chicken embryo dermal cells), patients with a history of allergy to eggs or egg products should not receive the vaccine.

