- have other acute, chronic, or exfoliative skin conditions (e.g., burns, impetigo, varicella zoster, severe acne, contact dermatitis, psoriasis, herpes or other open rashes or wounds), until the condition resolves.

- are pregnant or intend to become pregnant (due to the potential risk of fetal vaccinia); or are breast-feeding (due to the potential risk of contact transmission and inadvertent inoculation). It is currently unknown if vaccinia virus or antibodies are excreted in breast milk. Patients (*i.e.*, vaccinees) should avoid fathering a child for at least 4 months following completion of therapy with the recombinant vaccine.
- are in close contact with children less than 3 years of age (due to the potential risk of contact transmission and inadvertent inoculation).
- are immunodeficient or immunocompromised (by disease or therapy), including individuals with HIV infection.

Additionally, do not administer the recombinant vaccinia vaccine if the vaccinee:

- has a moderate or severe acute illness, until the illness resolves.
- is undergoing topical steroid therapy for inflammatory eye diseases, or undergoing therapy with systemic steroids; potential immune suppression increases risk for vaccinia-related complications.
- At this time, until a more definitive causal relationship is determined, it is recommended that patients with known CHF or clinically significant cardiomyopathy, not be vaccinated with recombinant vaccinia-based vaccines, due to the potential for development of myocarditis and/or pericarditis.

Although the CDC believes that there is no evidence to conclude that the licensed vaccinia vaccine used in the Smallpox Vaccination Program causes angina or heart attacks, it acknowledges a possible causal relationship between the vaccination and heart inflammation. The CDC continues to study the relationship, but in the meantime, recommends excluding individuals with underlying heart disease from participation in the current Smallpox Vaccination Program. Patients are being immunized with recombinant vaccinia vaccines with therapeutic intent and will be evaluated for cardiovascular risk factors and recent or symptomatic cardiac events per protocol eligibility criteria. Patients will be encouraged to minimize cardiovascular disease risks and encouraged to follow risk reduction according to standard medical practice.

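### The fathering precaution ends one month after the last dose in 2.1.1.16 and 7.4.1.1 but runs at least 4 months in 11.1.6 and 11.2.6, and nothing says which governs

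*Combined protocol and SAP*

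**What the plan says.** Four places in the combined protocol and SAP set a post-treatment reproductive precaution.

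- Section 2.1.1.16 (inclusion criterion) requires adequate contraception "for the duration of study therapy and at least one month post therapy".
- Section 7.4.1.1, on exposure through the father, states: "Male patients should refrain from fathering a child or donating sperm during the study and for one month after the last dose of PROSTVAC".
- Section 11.1.6 (fowlpox vector), addressed to site staff: "Instruct patients to avoid fathering a child for at least 4 months following therapy completion with the recombinant vaccine".
- Section 11.2.6 (vaccinia vector): patients "should avoid fathering a child for at least 4 months following completion of therapy with the recombinant vaccine".

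Section 7.4.1.1 also limits which partner pregnancies are recorded. It covers those "occurring from the date of the first dose until one month after the last dose should, if possible, be followed up and documented". Section 2.1.1.16 adds only that if a woman becomes or suspects she is pregnant "while her partner is participating in this study, she should inform her treating physician immediately".

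When a man is off study matters here. Section 3.7.2 allows exit at the patient's request, or by transfer to a long-term protocol once off treatment, with no minimum time after the last dose. Section 6.2.1.1 says that starting androgen deprivation leads to removal from the trial, although its next sentence says only that it may. Before removal, under 3.7, "effort must be made to have all subjects complete a safety visit approximately 28 days following the last dose of study therapy"; 3.8 asks, where feasible, "for a safety visit within 4-5 weeks of drug discontinuation". Otherwise Appendix C (footnote 7, both arms) continues follow-up past Cycle 9 until progression or a clinical need for androgen deprivation.

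**The concern.** The same precaution has two durations, and no text ranks or reconciles them. Staff working from Section 7 and staff working from Section 11 could give patients different instructions. A man released under 7.4.1.1 could still be restricted under Section 11.

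The protocol itself says the effects on a developing fetus are unknown (2.1.1.16). A partner pregnancy arising after the first month need not be documented under 7.4.1.1, so the trial could miss the information that would show whether the longer precaution is needed. What is at stake is consistent reproductive-safety instruction and data, not the efficacy comparison.

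**Working it through.** The protocol gives no figure to reproduce here. The check sets the two durations side by side and measures the gap under each reading of the wording.

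**Inputs.** One month is taken as 365.25/12 = 30.44 days and four months as 121.75 days (an assumption; by calendar, the difference between four months and one month is 89 to 92 days). The day count starts at the last dose.

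**Anchor.** Section 7.4.1.1 counts from the last dose. Section 11 counts from therapy completion, which it does not define. The last item of 3.7.1 describes completion of protocol therapy as including the roughly 28-day safety visit. So the Section 11 period starts at A = 0 (last dose) or A of about 28 (safety visit), and ends at E = A + 121.75, which is day 121.75 or day 149.75.

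**Release under 7.4.1.1.** If 'during the study' means being on study, release is the later of the off-study day S and day 30.44. Then gap = max(0, E - max(S, 30.44)).

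| Off-study day S | Gap, A = 0 | Gap, A = 28 |
|---|---|---|
| Within one month | 121.75 - 30.44 = 91.3 | 149.75 - 30.44 = 119.3 |
| 35 (5-week safety visit) | 121.75 - 35 = 86.75 | 149.75 - 35 = 114.75 |
| 84 (Cycle 9 Day 1, last dose Cycle 6 Day 1, 3 x 28) | 37.75 | 65.75 |
| 121.75 | 0 | 28 |
| 149.75 or later | 0 | 0 |

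The day-84 row is nominal. The Cycle 6 dose may move by 14 days either way and visits may be delayed by 2 weeks (Appendix C), so the interval can run from 84 - 14 = 70 to 84 + 14 + 14 = 112 days. With A = 0 the gap is then 51.75 down to 9.75 days.

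If 'during the study' means during treatment, release is at day 30.44 for everyone, and the first row applies to every man.

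**Pregnancy capture.** The 7.4.1.1 window closes one month after the last dose whether or not the man remains on study.

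- A = 0: uncovered share = (121.75 - 30.44)/121.75 = 91.3/121.75 = 75%.
- A = 28: uncovered share of the time from last dose to E = (149.75 - 30.44)/149.75 = 119.3/149.75 = 80%.

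This concerns which new pregnancies are captured. For those inside the window, 7.4.1.1 asks that the outcome be followed where possible.

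**The case against.** The best defence is that the passages can all be obeyed at once. A man who waits 4 months satisfies every one, 2.1.1.16 and Section 11 are worded as minimums, and 11.1.6 is a direct instruction to sites. A site that follows the whole protocol would give the 4-month instruction. This stands to the extent that nothing tells a site to permit fathering before month 4, so a reader should not infer such a permission. It does not remove the conflict: 7.4.1.1 gives a fixed end point rather than a minimum.

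A second defence is that the 4 months belongs to vaccinia, which is given once in week 1. That fails, because the fowlpox section carries the same 4 months and fowlpox is given through the last dose and in maintenance.

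A third is that most men stay on study, so their restriction outlasts 4 months. That is the default under Appendix C and closes the restriction gap for them if 'during the study' means on study. It does not help men who exit sooner, and it does not extend the capture window for anyone.

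On capture, Section 11 sets no window of its own, so the one-month window contradicts no stated rule; the mismatch follows from the two durations. There is also a partial backstop. Unanticipated problems that place subjects or others at greater risk are reportable with no post-dose cut-off (7.1.10, 7.2.1, 7.3.2). That covers unexpected, possibly related harm, not every pregnancy.

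**Conclusion.** The inconsistency is real and should be fixed. One month (2.1.1.16, 7.4.1.1) and at least 4 months (11.1.6, 11.2.6) are unreconciled. Counted from the last dose, the gap is about 3 months for any man off study within a month of that dose, whether by request, transfer or starting androgen deprivation. It reaches every man if 'during the study' means during treatment. The exact number of days depends on the undefined anchor: about 91 from the last dose, about 119 from a 28-day safety visit. Most of the 4-month precaution has no pregnancy capture under 7.4.1.1, for all men.

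Three stronger readings are not supported.

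- A reader might infer that one month is unsafe and 4 months is correct. The documents do not show which is right. The four-week window in 11.2.6 concerns fetal vaccinia after vaccination in pregnancy or shortly before conception, so it does not settle paternal exposure either way. Fowlpox is described as unable to replicate in non-avian species (11.1).
- A reader might infer that patients were given the wrong instruction. The consent pages and Appendix B are not in the review copy, so this cannot be checked.
- A reader might infer a known number of exposed men. The documents give none, and all participants had prior definitive surgery or radiation (2.1.1.2) with residual fertility unstated.

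The primary analysis is not affected.

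**What to change.** State one duration and one anchor throughout.

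- Unless the sponsor justifies one month, change 2.1.1.16 and 7.4.1.1 to a minimum of 4 months after the last PROSTVAC dose, counting maintenance doses and applying whether or not the man is still on study.
- Use the same last-dose anchor in 11.1.6 and 11.2.6, in place of therapy completion.
- Extend the 7.4.1.1 pregnancy-capture window to the same point.
- Check that the consent form and Appendix B agree.
- If the sponsor can justify one month, amend 11.1.6 and 11.2.6 instead and give the reason.

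The cost of the 4-month option is wording changes, a patient-information update if those documents say one month, and about 3 more months of contraception and pregnancy capture after the last dose.

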7.5 SAFETY REPORTING CRITERIA TO THE PHARMACEUTICAL COLLABORATORS

7.5.1 Reporting to Bavarian Nordic, Inc.

All events listed below must be reported in the defined timelines to [contact].

The CCR Office of Regulatory Affairs will send all reports to the manufacturer as described below.

The sponsor should also submit all safety reports that are sent to the FDA using the Medwatch 3500 Form to:

Bavarian Nordic, Inc.
Email: [contact];
Fax number for pharmacovigilance at BN: [contact]
Attention: [name]

7.6 INSTITUTIONAL BIOSAFETY COMMITTEE (IBC) REPORTING CRITERIA

7.6.1 Serious Adverse Event Reports to IBC

The site Principal Investigator (or delegate) will notify the site's IBC of any unexpected fatal or life-threatening experience associated with the use of PROSTVAC Vaccine as soon as possible but in no event later than 7 calendar days of initial receipt of the information. Serious adverse events that are unexpected and associated with the use of the PROSTVAC Vaccine, but are not fatal or life-threatening, much be reported to the IBC as soon as possible, but not later than 15 calendar days after the investigator's initial receipt of the information. Adverse events may be reported by using the FDA Form 3500a.

7.6.2 Annual Reports to IBC

Within 60 days after the one-year anniversary of the date on which the IBC approved the initial protocol, and after each subsequent anniversary until the trial is completed, the information described below shall be submitted. Alternatively, the IRB continuing review report can be sent to the IBC in lieu of a separate report. Please include the IBC protocol number on the report.

7.6.2.1 Clinical Trial Information

A brief summary of the status of the trial in progress or completed during the previous year. The summary is required to include the following information:

- the title and purpose of the trial
- clinical site
- the Principal Investigator
- clinical protocol identifiers;
- participant population (such as disease indication and general age group, e.g., adult or pediatric);
- the total number of participants planned for inclusion in the trial; the number entered into the trial to date whose participation in the trial was completed; and the number who dropped out of the trial with a brief description of the reasons
- the status of the trial, e.g., open to accrual of subjects, closed but data collection ongoing, or fully completed,
- if the trial has been completed, a brief description of any study results.

7.6.2.2 Progress Report and Data Analysis

Information obtained during the previous year's clinical and non-clinical investigations, including:

- a narrative or tabular summary showing the most frequent and most serious adverse experiences by body system
- a summary of all serious adverse events submitted during the past year
- a summary of serious adverse events that were expected or considered to have causes not associated with the use of the gene transfer product such as disease progression or concurrent medications
- if any deaths have occurred, the number of participants who died during participation in the investigation and causes of death
- a brief description of any information obtained that is pertinent to an understanding of the gene transfer product's actions, including, for example, information about dose-response, information from controlled trials, and information about bioavailability.

